GI	Gastrointestinal
GOLD	Global Obstructive Lung Disease
HBV	Hepatitis B virus
HCG	Human chorionic gonadotropin
HCV	Hepatitis C virus
HE	Hepatic encephalopathy
HIV	Human immunodeficiency virus
HNA2	Human nonmercaptalbumin-2
HR	Heart rate
HRS	Hepatorenal Syndrome
IB	Investigator's Brochure
ICA	International Club of Ascites
ICF	Informed consent form
ICH	The International Council for Harmonisation of Technical Requirements
	for Pharmaceuticals for Human Use
ICU	Intensive care unit
INR	international normalized ratio

23 of 87 Effective Date 24-Sep-2020 Page Effective
 Number
 GLB-PRT-ALB-IG1601
 Version
 6.0
 Status
 Effective control

 IG1601 - Prevention of Mortality with Long-Term Administration of Human Albumin in Subjects with
 0.0
 Status
 Effective control
 Decompensated Cirrhosis and Ascites **GRIFOLS Bioscience Industrial Group**

IP	Investigational product
IRB	Institutional Review Board
ITT	Intent-to-treat
IUD	Intrauterine device
IV	Intravenous
LDH	Lactate dehydrogenase
MAP	Mean arterial pressure
MedDRA	Medical Dictionary for Regulatory Activities
MELD	Model for End-stage Liver Disease
NA	North America
NYHA	New York Heart Association
OPTN	Organ Procurement and Transplantation Network
PH	Proportional-Hazards
PP	Per-protocol
PRA	Plasma renin activity
RR	Respiratory rate
SAE	Serious adverse event
SAP	Statistical analysis plan
SBP	Spontaneous bacterial peritonitis
SD	Standard deviation
SMT	Standard medical treatment
SOP	Standard operating procedures
SPO ₂	Peripheral capillary oxygen saturation
Т	Temperature
TIPS	Transjugular intrahepatic portosystemic shunt
TEAE	Treatment-emergent adverse event
ULN	Upper limit of normal
WBC	White blood cells

1 GENERAL INFORMATION

Protocol title and other key study information are provided on the title page. Information regarding additional key personnel and organizations involved in the conduct of the study, including names and contact details of participating investigators, monitors, clinical laboratories, technical departments and/or institutions, as well as information on members of additional study committees, will be found in the study files of the sponsor and at the investigator study centers within the study reference manual/file.

Investigators and staff will receive training either via an investigators meeting or other appropriate individual study center training session(s).

Data Safety Monitoring Board

A Data Safety Monitoring Board (DSMB) will be established for this clinical study to monitor the progress and the safety of the clinical study participants. The DSMB Charter will outline the DSMB composition, responsibilities, schedule of the DSMB meetings, and study stopping rules.

2 BACKGROUND INFORMATION

In addition to the information provided below, please also refer to the Investigator's Brochure (IB) (1) and any additional data supplied by the sponsor.

2.1 Name and Description of the Investigational Product

The investigational product (IP) in this study is Albumin (human) USP, 20% (Albutein[®] 20%), which will be administered as a treatment for decompensated cirrhosis and ascites. Albutein 20% is a solution containing 200 g/L of total protein of which at least 95% is albumin. See Section 4.4 for study treatments details.

Standard medical treatment (SMT) will be administered per institution standards. There are several published guidelines for the treatment and management of patients with decompensated cirrhosis (2-5).

2.2 Relevant Findings from Nonclinical and Clinical Studies

Effects of Long-term Human Albumin Treatment in Subjects with Decompensated Cirrhosis

Several studies assessing the effect of long-term human albumin treatment in subjects with decompensated cirrhosis have been reported (6-15). In one study, the effect of intravascular volume expansion with human albumin treatment in subjects with cirrhosis and ascites was evaluated. Hospitalized subjects were randomized to receive diuretics alone or diuretics + human albumin (12.5 g/day during hospitalization followed by 25 g/week after discharge) and were followed for a median duration of 20 months. Overall, human albumin treatment was more effective than diuretics alone in resolving ascites and reducing the length of the hospital stay; however, these results were only achieved in a subset of subjects receiving a low dose of diuretics (13).

In a second study, the effects of long-term human albumin administration on survival, recurrence of ascites, and onset of other complications were examined. Subjects hospitalized for first-onset ascites were randomized to receive diuretics alone or diuretics + human albumin (25 g/week for the first year, then 25 g every 2 weeks) and were followed for a median time of 84 months (range 2 to 120 months). In the study, subjects receiving human albumin had a significantly reduced recurrence rate of moderate to severe ascites and reduced rate of mortality (14).

A third study is a non-profit open-label, multicenter, randomized clinical study, sponsored by the Agenzia Italiana del Farmaco (AIFA) (Long-Term Use of Human Albumin for the Treatment of Ascites in Patients with Hepatic Cirrhosis: a Multicenter, Open-label Randomized Clinical Trial: The Interim Analysis of the ANSWER Study). In this study, the effectiveness of long-term human albumin administration on mortality, quality of life, and onset of other complications is being examined in subjects with cirrhosis and uncomplicated ascites (no renal failure or refractory ascites) receiving at least 200 mg per day of an anti-mineralocorticoid drug and 25 furosemide per day. Subjects are randomized to receive diuretics alone or diuretics + human albumin (40 g twice a week for 2 weeks, then 40 g/week for up to 24 months) (15).

Interim analysis of data from 386 out of a planned 420 subjects in the ANSWER study suggests that long-term human albumin administration significantly improves the management of ascites and is also able to reduce the incidence of other severe clinical complications of the disease to prolong survival in subjects with decompensated cirrhosis (15).

2.3 Known and Potential Risks and Benefits to Human Subjects

Administration of albumin has shown efficacy in prevention and treatment of circulatory dysfunction in cirrhosis (16). Paracentesis is the most used treatment in cirrhotic patients with ascites but can cause a worsening of circulatory dysfunction. Administration of albumin after paracentesis can prevent this circulatory dysfunction (17). In patients with spontaneous bacterial peritonitis (SBP), the administration of intravenous (IV) albumin improves their circulatory function, reduces the presence of hepatorenal syndrome (HRS) from approximately 30 to 10% (9), and improves patient survival (14). The administration of albumin together with vasoconstrictors reverses the circulatory dysfunction and normalizes the serum concentration of creatinine to 40 to 60% in patients with HRS type 1 and improves their survival (18,19). There are also data that suggest that long term albumin administration (25 g weekly) improves the control of ascites and reduces the incidence and intensity of the muscle cramps (20).

Based on these studies, long-term administration of human albumin has potential beneficial effects on circulatory dysfunction, inflammatory response, oxidative stress, organ dysfunction, and organ failure. Long-term treatment with human albumin was initially proposed for the management of patients with decompensated cirrhosis with ascites based on its oncotic properties. In patients with cirrhosis and portal hypertension, ascites formation is the consequence of effective hypovolemia, which promotes renal retention of sodium and water. The preservation of the central blood volume with human albumin represents a logical

approach for the management of cirrhotic patients with ascites since it would improve renal function and the response to diuretics (21).

Long-term human albumin administration may improve circulatory and organ function not only by directly acting as plasma-expander, but also indirectly modulating the deleterious effects of immune dysfunction and chronic or acute inflammation on the systemic circulation and organ function. Intravenous human albumin administration in decompensated cirrhosis increases cardiac contractility and systemic vascular resistances through the effects related to its non-oncotic properties. Maintaining an effective blood volume may support adequate organ perfusion and avoid/delay the occurrence of organ impairment/failure (21).

In addition, long-term human albumin administration may also modulate the deleterious effects of inflammatory mediators on mitochondrial and cell function and on organ microcirculation, thus protecting target organs against tissue damage and microcirculatory disturbances. These effects could potentially reduce the incidence of decompensation episodes (ie, ascites, renal or liver failure, hepatic encephalopathy (HE), severe sepsis, septic shock, and acute-on-chronic liver failure [ACLF]) and increase survival rates (21).

Albutein is made from pooled human plasma. Based on effective donor screening and product manufacturing processes, it carries an extremely remote risk for transmission of viral diseases, including a theoretical risk for transmission of Creutzfeldt-Jakob disease (CJD). Although no cases of transmission of viral diseases or CJD have ever been identified for albumin, the risk of infectious agents cannot be totally eliminated (1).

Albutein is contraindicated in patients with severe anemia or cardiac failure in the presence of normal or increased intravascular volume. The use of Albutein is contraindicated in patients with a history of allergic reactions to this product. The most serious adverse reactions (ARs) are anaphylactic shock, heart failure, and pulmonary edema. The most common ARs are anaphylactoid type reactions. For additional information on potential risks and adverse events (AEs), please also refer to the IB (1) and any additional data supplied by the sponsor.

2.4 Description of and Justification for the Route of Administration, Dosage, Dosage Regimen, and Treatment Periods

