5.2 Exclusion Criteria

A subject meeting any of the following exclusion criteria is NOT eligible for participation in the study.

1v5. Subjects with ACLF at Screening.

87 Ъ 24-Sep-2020 30 Effective Date Page Effective
 Number
 GLB-PRT-ALB-IG1601
 Version
 6.0
 Status
 Errect

 IG1601 - Prevention of Mortality with Long-Term Administration of Human Albumin in Subjects with
 6.0
 Status
 errect
Version 6.0 Decompensated Cirrhosis and Ascites GRIFOLS **Bioscience Industrial Group**

- 2v5. Subjects with type 1 HRS currently on treatment with vasoconstrictors or hemodialysis.
- 3. Subjects with TIPS or other surgical porto-caval shunts.
- 4v5. Subject with refractory ascites as defined by ICA criteria without any other event of acute decompensation (Appendix 2).
- 5v5. This criterion has been removed from protocol Version 5.
- 6v5. Subjects receiving dual anti-platelet therapy or anti-coagulant therapy (exception: DVT prophylaxis).
- 7v5. Subjects with ongoing endoscopic eradication of esophageal varices with ≤ 2 endoscopic sessions completed before screening.
- 8v5. This criterion has been removed from protocol Version 5.
- Subjects with evidence of current locally advanced or metastatic malignancy. Subjects with hepatocellular carcinoma within the Milan criteria [1 nodule ≤5 cm or 3 nodules ≤3 cm] [Appendix 6], non-melanocytic skin cancer, or controlled breast or prostate cancer can be included.
- 10v4. Subjects with acute or chronic heart failure (New York Heart Association [NYHA] Appendix 7).
- 11. Subjects with severe (grade III or IV) pulmonary disease (Global Obstructive Lung Disease [GOLD] Appendix 8).
- 12v5. Subjects with nephropathy with renal failure with a serum creatinine $\geq 2 \text{ mg/dL}$ or systemic hypertension.
- 13v5. This criterion has been removed from protocol Version 5.
- 14. Subjects with severe psychiatric disorders.
- 15. Subjects with a known infection with human immunodeficiency virus (HIV) or have clinical signs and symptoms consistent with current HIV infection.
- 16. Females who are pregnant, breastfeeding, or, if of childbearing potential, unwilling to practice effective methods of contraception (oral, injectable, or implanted hormonal methods of contraception, placement of an intrauterine device (IUD) or intrauterine system, condom, or occlusive cap with spermicidal foam/gel/cream/suppository, male sterilization, or true abstinence*) throughout the study.

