 - * True abstinence: When this is in line with the preferred and usual lifestyle of the subject (periodic abstinence [eg, calendar, ovulation, symptothermal, post-ovulation methods], declaration of abstinence for the duration of the clinical study, and withdrawal are not acceptable methods of contraception).
- 17. Subjects with previous liver transplantation.
- 18. Subjects with known or suspected hypersensitivity to albumin.
- 19. Subjects participating in another clinical study within 3 months prior to screening.
- 20v4. Subjects with active drug addiction (exceptions: active alcoholism or marijuana)
- 21. In the opinion of the investigator, the subject may have compliance problems with the protocol and the procedures of the protocol.

- 22. Subjects with ongoing or recent variceal bleeding. (subjects can be included 2 weeks after hemorrhagic episode).
- 23. Subjects with septic shock at screening.
- 24. Subjects with ongoing SBP infection (subjects can be included upon resolution).
- 25. Subjects with current infection of COVID19, those who are less than 14 days post recovery, or those who have clinical signs and symptoms consistent with COVID19 infection.

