5.3.2 Discontinuation of Subjects from Treatment

If a subject receives a liver transplant, study treatment and all treatment-related assessments will be discontinued upon transplant. The criteria to determine when a subject becomes a candidate for liver transplantation is described in Section 5.3.2.1. The subject will continue to have subsequent planned visit assessment procedures performed.

Discontinuation of the treatment in subjects who receive a TIPS insertion will be at the discretion of the investigators. In case it is decided to discontinue the subject's treatment early, study treatment will be stopped and the subject will continue to have subsequent planned visit assessment procedures performed.

Adverse events that will determine temporary subject's discontinuation from study treatment include the following:

• Subjects developing severe bleeding, Albutein 20% infusions will be temporarily stopped until the bleeding episode is resolved. For subjects with variceal bleeding, Albutein 20% infusions will be temporarily stopped until the subject has received at least 2 banding sessions. Albutein 20% infusions will be resumed after the bleeding episode is resolved or after the subject has received at least 2 banding sessions, respectively.

Adverse events that will determine permanent subject's discontinuation from study treatment include the following:

- Anaphylactic shock or transfusion-related acute lung injury
- Severe AEs (ie, acute myocardial infarction, cerebral hemorrhage, cardiac failure, pulmonary edema, or intestinal necrosis) that precludes the continuation of the subject in the clinical study

Subjects with any one of these severe AEs will be discontinued from study treatment and all treatment-related assessments, and should continue to have subsequent planned visit assessment procedures performed.

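### Severe anemia with normal or raised intravascular volume is a stated contraindication to Albutein, yet it is not an exclusion criterion and the rule for restarting infusions after a bleed makes no exception for it

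*Protocol*

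**What the plan says.** Protocol 2.3 gives the product's contraindications. The main sentence is: "Albutein is contraindicated in patients with severe anemia or cardiac failure in the presence of normal or increased intravascular volume". The next sentence adds previous allergic reactions to the product. The section then lists the gravest risks: "The most serious adverse reactions (ARs) are anaphylactic shock, heart failure, and pulmonary edema".

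Protocol 5.2 turns two of these conditions into exclusions: 10v4, "Subjects with acute or chronic heart failure", and 18, "Subjects with known or suspected hypersensitivity to albumin". Two other exclusions bear on bleeding. 7v5 covers "Subjects with ongoing endoscopic eradication of esophageal varices" when 2 or fewer sessions have been completed. 22 covers ongoing or recent variceal bleeding and allows entry 2 weeks after the episode.

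Protocol 5.3.2 holds infusions during severe bleeding and then says: "Albutein 20% infusions will be resumed after the bleeding episode is resolved or after the subject has received at least 2 banding sessions, respectively".

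**The concern.** Sites enroll from the criteria in 5.1 and 5.2 and dose from 5.3.2 and 6.1.1. A contraindication found only in the background section has to be remembered, and applied over operational text that says something else. Two of the three conditions in 2.3 were carried into the exclusions and one was not, although severe anemia stands in the same sentence as cardiac failure.

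The restart rule is where this matters most. A subject who has just bled may well be anemic, and may have had volume restored during treatment. That is when 5.3.2 has infusions begin again. Bleeding is foreseeable in this population: Protocol 2.6 names gastrointestinal bleeding among the complications subjects may present, and 8.3.10 lists it as anticipated disease progression. What is at stake is the safety of individual subjects, not the validity of the efficacy comparison.

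**Working it through.** No arithmetic bears on this point, so the check sets the provisions side by side.

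**1. Contraindications in 2.3 against exclusions in 5.2**

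| Condition in 2.3 | Matching exclusion |
|---|---|
| Cardiac failure, with the volume condition | 10v4, written without any volume condition |
| Previous allergy to the product | 18 |
| Severe anemia, with the volume condition | None |

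The inclusion and exclusion criteria in the synopsis and in 5.1 and 5.2 contain no mention of anemia, hemoglobin or intravascular volume. The volume condition does not explain the omission, because cardiac failure carries the same condition in 2.3 and was excluded outright.

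**2. Nearest entry criteria.** Exclusions 7v5 and 22 concern varices and variceal bleeding. They make a recently bled, anemic entrant less likely. Neither sets a hemoglobin condition, and a subject becomes eligible under 22 by the passage of 2 weeks alone.

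**3. Restart rule.** The triggers in 5.3.2 are resolution of the bleed or, for variceal bleeding, at least 2 banding sessions. Neither refers to hemoglobin or volume, and no exception is written.

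**4. Does the volume condition empty the category?** Protocol 2.3 says that "ascites formation is the consequence of effective hypovolemia", which argues for few cases at baseline. But 2.3 also describes albumin as preserving central blood volume, 6.1.1 repeats the infusion about every 10 days for up to 12 months, and 6.2.4 provides for cardiac overload and pulmonary edema. Hypovolemia at entry therefore cannot be assumed at every later infusion.

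**5. Is a current hemoglobin to hand at restart?** Table 7-1 includes hemoglobin in the hematology panel. The schedule in Protocol Appendix 1 takes clinical laboratory samples at screening, Day 1, Day 11, the monthly visits and Month 12 or early discontinuation. The 23 intermediate infusion days listed in 7.2.1.2.3 have none. SAP 8.4 expects 37 infusions for a completer, so 37 − 23 = 14 infusion days have a scheduled sample. Monthly visits are 30 days apart (for example Days 31 and 61), so the latest scheduled hemoglobin may predate a bleed. A restart check therefore has to specify a value taken after it.

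**The case against.** The best answer is that the restriction is already in the protocol. Section 2.3 binds the investigator, and 2.3 and 8.3.1 both refer to the Investigator's Brochure. Nothing in 5.3.2 says that resumption overrides 2.3 or sets a deadline for it. Other text assumes that infusions can be cut short or stopped for other reasons: 6.3 requires reasons when less than the full prepared dose is given, 5.3.3 allows withdrawal on the investigator's judgment, 8.2.3 has out-of-range results reviewed for clinical significance, and SAP 10.1 tabulates events leading to drug interruption or withdrawal. Exclusions 7v5 and 22 and the hold during severe bleeding narrow the group further.

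Most of this stands, and it is why the number affected is probably small. It does not close the gap. None of these provisions is an entry or dosing rule for anemia: 8.2.3 serves adverse event reporting, and 5.3.3 is discretionary. A careful investigator would reach the right decision, but by setting background text against an explicit restart instruction.

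Three stronger readings are tempting and are not supported:

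- **That the plan doses anemic subjects against its own contraindication in general.** The contraindication, as read here, needs severe anemia together with normal or raised volume. Anemia alone is not enough.
- **That the permanent-stop list in 5.3.2 is deficient because anemia is missing.** That list contains all three of the most serious reactions named in 2.3. The absence of anemia from it is not a gap.
- **That the size of an infusion measures the risk.** The dose is the same for any subject of a given weight and says nothing about how often the contraindicated state occurs.

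**Conclusion.** The point holds as an inconsistency between 2.3 and the rules that sites follow: one of three stated contraindications is absent from the exclusions, and the restart rule has no exception for it. It is a cheap improvement for patient safety. It has no bearing on the sample size, the error rate or the primary analysis.

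The number of subjects affected is unknown, because the documents give no distribution of hemoglobin or volume status. It is probably small.

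The conclusion rests on two assumptions. First, the volume condition in 2.3 is read as applying to severe anemia as well as to cardiac failure; if it applied only to cardiac failure, the uncovered group would be wider. Second, the Investigator's Brochure, DSMB charter and pharmacy manual were not available and may contain controls that reduce the practical gap.

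**What to change.** Make two additions to the protocol.

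- **In 5.2 (and the synopsis):** exclude subjects with severe anemia when intravascular volume is normal or increased, as judged by the investigator from clinical volume status and the local screening blood count.
- **In 5.3.2:** hold infusions, and do not resume them after a bleed, while that condition is present. Judge it from a hemoglobin taken after the bleed, either in routine care or at a scheduled visit.

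The volume condition should stay in both, so that anemia alone does not bar entry or treatment. Any numeric hemoglobin threshold is for the sponsor's clinical team; the documents give none.

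The cost is an amendment and possibly a few screen failures or held infusions. At entry the burden is slight, because 7.2.1.1 already checks eligibility on local laboratory results, and the CLIF-C AD score in Appendix 3 needs a white cell count; the documents do not, however, list the local tests. After a bleed, hospital results would usually be expected to supply the value. If none exists, the restart waits for the next routine or scheduled result, so no study visit or blood draw need be added.

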2.4.1 Administration of Investigational Products

Albutein 20% will be infused at a dose of 1.5 g/kg body weight (maximum 100 g per subject) every 10 ± 2 days for the duration of study participation (up to 12 months).

